Data from subjects and clinical readers can be obtained prospectively, or existing data can be used. An obvious difference between prospective collection of images and collection of existing images is that the clinical reader of the existing images would likely be unaware that his/her image interpretation would be used in a clinical study, whereas in prospective image reads the clinical reader would obviously be aware that his/her interpretation will be collected for the study. This will not affect the study results because the clinical interpretation would still be conducted blinded to the expert image read (which will occur after the clinical image read in every case). Indeed, similar studies of other amyloid imaging agents (Amyvid (florbetapir) and Neuraceq (florbetaben) are designed to use existing images to test clinical readers [EUPAS11867], [EUPAS12145].

Data sources will be the images and patient medical records. Image interpretations and other data will be recorded directly onto eCRFs; images will be provided electronically. All measurements are considered standard for assessment of a diagnostic test.

Each image interpretation will be compared to the corresponding majority blinded visual interpretation of 5 expert readers and sub-classified as true positive (TP), true negative (TN), false positive (FP), or false negative (FN). Expert image reads will be obtained prospectively from expert readers who consent to participate.

Diagnostic accuracy (the percentage of all images correctly interpreted) will be determined based on all images. Since the maximum possible value of diagnostic accuracy is 1, one minus the diagnostic accuracy will give the overall rate of image interpretation errors.

The standard measures of diagnostic test performance, sensitivity (TP rate for image interpretation), and specificity (TN rate for image interpretation), will also be determined based on all images. Other study endpoints will include PPV and NPV.

All of the above metrics will be determined for subsets of images by country and by reader. Further details may be found below in the body of the protocol.

Population

At least 200 VIZAMYLTM images will be collected from at least 200 subjects. Subjects will be patients who are being (or have been) evaluated for AD and other causes of cognitive impairment, who are referred (or were referred) by their physician for a clinically indicated VIZAMYLTM PET brain scan.

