Data sources

Data from subjects and clinical readers can be obtained prospectively, or existing data can be used. The clinical interpretations of existing images collected will be obtained from the patient medical record. Expert reads will be obtained prospectively from expert readers who consent to participate. Data sources will be the images and patient medical records. Image interpretations and other data will be recorded directly onto electronic case report forms (eCRFs); images will be provided to the Sponsor electronically. All measurements are considered standard for assessment of a diagnostic test.

Study size

At least 200 VIZAMYLTM images collected from at least 200 subjects will be interpreted by clinical readers from the institution where the images were obtained (i.e., each reader will interpret only those images collected at his/her institution). The readers' interpretations will be compared to the majority blinded visual interpretations of the same images made subsequently by 5 expert readers to determine diagnostic accuracy, sensitivity, specificity, PPV, and NPV.

Data analysis

Diagnostic accuracy, sensitivity, specificity, PPV, and NPV value will be determined for each reader, and reported as point estimates with exact 95% confidence intervals (CIs).

Milestones

[figure not shown]
| Milestone | Planned date |
|-------------------------------------|----------------|
| Registration in the EU PAS register | |
| Start of data collection | |
| End of data collection | |
| Final report of study results | |
| Study progress reports | Twice annually |

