9.2.5 Selection and Replacement of Clinical Readers

Each potential clinical reader contacted will be asked to complete a screening survey, which asks, among other things, if they are willing to participate in the study, and if they are authorised by their institution to read VIZAMYLTM PET images. Those who meet eligibility criteria and are willing to participate will be included in the study, 1 to 5 clinical readers per country.

To avoid overrepresentation of any reader, institution, or country in the study results, the following restrictions will apply:

- No clinical reader may contribute more than 7.5% of the total number of images (e.g., 15 of 200 images)
- No institution may contribute more than 15% of the total number of images (e.g., 30 of 200 images)
- No country may contribute more than 25% of the total number of images (e.g., 50 of 200 images)

Page 23 of 43

Additional clinical readers may be added as necessary to replace clinical readers who withdraw. In the event that a clinical reader withdraws, the reason for withdrawal will be recorded, and permission to use his/her data will be sought; if declined, he/she will be replaced and his/her data will not be used.

GE-067-027 C

Version 7.0 Approved

9.2.6 **Selection and Replacement of Expert Readers**

The expert readers will consist of 5 experienced nuclear medicine physicians or radiologists, with extensive experience in PET imaging (including VIZAMYLTM imaging), who have completed the VIZAMYLTM training programme. They may have participated in VIZAMYLTM clinical trials. The expert readers will have a minimum of 5 years of experience in nuclear medicine brain imaging and must have reviewed a minimum of 100 amyloid PET images within the previous 5 years from the start of the study.

In the event that an expert reader withdraws, the reason for withdrawal will be recorded. If the expert reader withdraws before reading all of the images, or withdraws permission to use his/her demographic information, he/she will be replaced. The replacement reader will be asked to read all images and his/her results will be used. The incomplete results from the expert reader who withdrew will not be used.

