9.5 Study Size

Number of Subjects

This study has no formal hypothesis and no statistical tests will be performed. The endpoints of accuracy, sensitivity, and specificity will be summarised descriptively with point estimates and

95% CIs. Although no formal hypothesis will be tested, the sample size is determined to achieve the desired precision in estimating the primary endpoint of the percentage of subjects whose images are correctly classified as positive or negative (accuracy). Assuming that VIZAMYLTM images from 90% of subjects are read correctly by readers who have taken the VIZAMYLTM training programme, 200 subjects will achieve a 95% CI width of less than 10%.

The endpoints of sensitivity and specificity will also be summarised descriptively. This study aims to characterise reader performance in clinical practice so the number of positive and negative images will not be controlled. However, it is expected that most patients who are referred for a VIZAMYLTM scan will have dementia, and most cases of dementia are AD. Since brain amyloid is present in AD, it is expected that the majority of patients in this study will have brain amyloid. It is assumed that the majority blinded interpretation of the expert readers will be SOT-positive for approximately 65% of scans, giving a total of approximately 130 scans for sensitivity, with the remaining 70 scans being SOT-negative and therefore usable for calculating specificity. Assuming a sensitivity of 90% and a specificity of 90%, these sample sizes should give reasonably precise 95% CIs for estimating sensitivity and specificity in this scenario (95% CI width of approximately 15% or less).

Accuracy, sensitivity, and specificity will also be calculated by country where all study images from sites within a given country will be pooled for analysis. No country may contribute more than 25% of the total number of images. Because the number of subjects per country is smaller than the overall number of subjects, the level of precision and the width of the CI will be impacted. Again, since the aim of the study is to characterise reader performance in clinical practice, the exact number of images obtained per country and per site is unknown. Table 6 provides examples of 95% CI widths for accuracy assuming a few different sample sizes per country to illustrate the change in precision.

Table 6 95% Confidence Interval Width for Different Sample Sizes Assuming 90% Diagnostic Accuracy

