| | | Lower Confidence | Upper Confidence |
|-------------|---------------------|------------------|------------------|
| Sample Size | Actual 95% CI Width | Limit | Limit |
| 30 | 24.4% | 73.5% | 97.9% |
| 40 | 20.9% | 76.3% | 97.2% |
| 50 | 18.5% | 78.2% | 96.7% |
| 60 | 16.7% | 79.5% | 96.2% |

When calculating sensitivity and specificity per country, precision will again be impacted because the sample size per country will be further divided into SOT-positive and SOT-negative scans. For example, if a country enrols 40 subjects and 65% of the scans are SOT-positive (n = 26) then the width of the 95% CI for sensitivity would be 26.4% (lower confidence limit = 71.8%) and the width for specificity would be 37% (lower confidence limit = 62.4%).

Accuracy by reader will also be presented in a tabular form, though it may be expected that some institutions will have very few scans per reader.

GE Confidential Page 27 of 43

Number of Clinical Readers

The number of clinical readers (1 to 5 per country) was chosen to allow each European country where VIZAMYLTM is commercially available to be represented.

Number of Expert Readers

The number of expert readers (5) was chosen based on precedent set in prior clinical studies of VIZAMYLTM.

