The by-variable summaries will include estimates of diagnostic accuracy, sensitivity, specificity, PPV, and NPV along with 95% CIs for data pooled within each category. They will also show the number of clinical readers in each category and the number and percentage of clinical readers in each category with diagnostic accuracy <70%, >70% to $\le80\%$, >80% to $\le90\%$, and >90%.

The certainty of image classification will be summarised.

Safety Analyses

The number and percentage of subjects with 1 or more treatment-emergent AEs will be summarised. Additionally, treatment-emergent AEs will be coded and summarised by system organ class and preferred term. Treatment-emergent AE summaries will be provided by relationship to study drug and severity. Treatment-emergent serious AEs (SAEs) will also be summarised.

Interim Analysis

No formal interim analyses of the data are planned for this study. Interim progress reports of enrolment and safety will be provided annually.

Analyses of Study Limitations

Please see Section 9.9 below.

Evaluation of Impact of Study Results on Marketing Authorisation

The Sponsor will evaluate whether the study results have an impact on the marketing authorisation and will, if necessary, submit to the EMA an application to vary the marketing authorisation.

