8.6.3 Secondary analysis

Images for which 5 expert readers agree, 4 expert readers agree, and 3 expert readers agree will be summarised using counts and percentages.

In addition, estimates of diagnostic accuracy, sensitivity, specificity, PPV, and NPV, along with exact 95% CIs, will be provided separately for prospective images, retrospective images, and pooled results, separately, using the following variables:

- Country
- Time from training to image interpretation (<6 months, \geq 6 months)
- Specialty of the reader
 - Nuclear Medicine
 - Radiology
 - Medical Physics
 - Other
- Training method (s) used by the clinical reader (in-person, electronic, or both)
- Number of scans read by the clinical reader in practice prior to the study (<50, \geq 50)
- Clinical reader and SOT classification certainty (1 to 5)

The number of clinical readers in the above subgroups will be provided. The number and percentage of diagnostic accuracy categories <70%, >70% to \leq 80%, >80% to \leq 90%, and >90% will also be provided by using the above subgroups for prospective images, retrospective images, and pooled results, separately.

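### Reader accuracy bands are formed within image-level splits (certainty, time from training, data source) where a reader may have only a few images, and exactly 70% falls in no band

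*Protocol*

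**What the plan says.** Protocol 9.7 (Secondary Analyses) gives, for each category of each subgroup variable, the "number and percentage of clinical readers in each category with diagnostic accuracy <70" per cent, above 70 up to 80%, above 80 up to 90%, and above 90%. The variables are country, time from training, specialty, training method, scans read before the study, and certainty from 1 to 5.

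SAP 8.6.3 keeps the four bands, adds the certainty of the standard of truth to the list, and says that the bands "will also be provided by using the above subgroups for prospective images, retrospective images, and pooled results, separately".

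Three other passages set how many images a reader can have. Protocol 9.2.5: "No clinical reader may contribute more than 7.5% of the total number of images (e.g., 15 of 200 images"). SAP 6.2 admits a reader with one classified image. Protocol 9.5 and SAP 5 expect that "some institutions will have very few scans per reader".

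On results by reader, the protocol abstract says that accuracy and the other measures "will be determined for each reader, and reported as point estimates with exact 95% confidence intervals". Protocol 9.5 and SAP 5 promise a table of accuracy by reader. SAP 8.6, which specifies the efficacy outputs, does not itemise it.

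**The concern.** A band count is informative only if each reader's observed accuracy rests on enough images to place the reader in a 10-point band with some confidence. Neither document sets a minimum number of images, attaches an interval to the band table, or says which images form a reader's accuracy when the category is a property of the image.

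Under certainty level 2, for example, there are two ways to read the plan. If accuracy is recomputed from the reader's level-2 images, the cell may hold one or two images. If it is the reader's overall accuracy, the same reader appears with the same band under every level used, and the table says nothing about certainty.

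The secondary objective is to look for factors associated with interpretation errors. Under the first reading, two categories can show different band counts merely because readers have different numbers of images in them.

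**Working it through.** **Inputs.** True accuracy 90% (Protocol 9.5: "Assuming that VIZAMYLTM images from 90% of subjects are read correctly"); total of at least 200 images, with no upper limit stated; reader cap 7.5%; reader minimum of one image (SAP 6.2).

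**The plan's own figures.** The cap is 0.075 × 200 = 15 images. It grows with the total: 0.075 × 250 = 18.75, so 18; 0.075 × 300 = 22.5, so 22. Exact (Clopper-Pearson) 95% intervals reproduce Protocol Table 6: 27/30 gives 73.5 to 97.9%, 36/40 gives 76.3 to 97.2%, 45/50 gives 78.2 to 96.7%, 54/60 gives 79.5 to 96.2%.

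**Which splits divide a reader's images.**

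| Variable | Property of | Divides one reader's images? |
|---|---|---|
| Country, specialty, training method, prior scans | Reader | No |
| Certainty 1 to 5 | Image | Yes |
| Time from training | Image date | Can |
| Prospective or retrospective | Image | Can |

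A reader at the cap of 15 who spread images evenly over five certainty levels would have 15/5 = 3 per level. This is an illustration; the documents do not forecast how the scale will be used.

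**Which bands can occur.** Observed accuracy is x/n. With n of 3 or less, only the bands below 70% and above 90% can occur. With n = 4 or 5 the band above 80 up to 90% is empty. With n = 6 the band above 70 up to 80% is empty. With n of 10 or less, exceeding 90% needs a perfect score.

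**Chance of each band at true accuracy 90%.** Binomial, X ~ Bin(n, 0.9). For n = 3, P(X ≤ 2) = 1 − 0.9³ = 0.271. For n = 5, P(X ≤ 3) = 1 − 0.9⁵ − 5(0.9⁴)(0.1) = 0.081.

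| n | <70% | exactly 70% | >70 to 80% | >80 to 90% | >90% |
|---|---|---|---|---|---|
| 3 | 27.1 | 0 | 0 | 0 | 72.9 |
| 5 | 8.1 | 0 | 32.8 | 0 | 59.0 |
| 10 | 1.3 | 5.7 | 19.4 | 38.7 | 34.9 |
| 11 | 1.9 | 0 | 7.1 | 21.3 | 69.7 |
| 15 | 1.3 | 0 | 17.1 | 26.7 | 54.9 |

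(Entries are percentages.) Between 10 and 11 images the chance of the top band doubles with no change in skill. In the other direction, a reader with true accuracy 75% scores 3 of 3 with probability 0.75³ = 42%.

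**Near the cap.** At n = 15 the chance of exceeding 90% is 8.0%, 31.9% and 82.9% for true accuracy 75%, 85% and 95%, so the bands do separate readers. An individual placement is still imprecise: the exact interval for 14/15 is 68.1 to 99.8%.

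**Noise against skill.** Let s be the between-reader standard deviation of true accuracy around a mean of 90%. The share of observed variance due to skill is s² / [s² + (0.09 − s²)/n]. The documents give no s. For assumed s of 3, 5, 8 and 10 points the share is 0.13, 0.30, 0.53 and 0.65 at n = 15, and 0.03, 0.08, 0.19 and 0.27 at n = 3. Noise exceeds skill when s is below 0.3/√(n + 1): 7.5 points at n = 15, 12.2 at n = 5, 15 at n = 3.

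**Gap at 70%.** As written in both documents, the lowest band ends below 70% and the next begins above it. A reader with 7 of 10 correct is counted nowhere. Ten images is an ordinary number: a country at its ceiling of 50 ("No country may contribute more than 25% of the total number of images (e.g., 50 of 200 images") with five readers averages 50/5 = 10 each.

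**The case against.** The other side has a good deal of weight.

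A reader might infer that the whole band table reflects image counts more than skill. The documents do not support that. It depends on a between-reader spread they do not give, four of the six protocol variables leave a reader's images intact, and near the cap the bands discriminate.

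A reader might also infer that a count below 70% would be largely chance, or would be taken as the share of readers for whom training failed. At 10 or 15 images a 90%-accurate reader falls there only 1.3% of the time, and the documents do not say how many readers will have three to five images. Neither document defines that band as training failure, and both allow untrained readers (Protocol 9.3.2, SAP 3.3).

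Nor has the SAP abandoned results by reader. SAP 3.1 and SAP 5 both mention them, SAP 8.6.1 applies exact intervals where applicable, and SAP 8.6.2 plans subject-level listings of reader evaluations. What is missing is an itemised output in SAP 8.6.

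Finally, the study is descriptive with no hypothesis test, and the pooled band tables remain. All of this stands. It narrows the point to the splits that divide a reader's images and to the gap at 70%; it does not answer either.

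**Conclusion.** The concern holds in limited form. SAP 8.6.3 applies the bands to splits that can cut one reader's images into cells too small for four bands. At three images or fewer two bands are impossible, and a 90%-accurate reader is placed below 70% with probability 27% at n = 3 and 8% at n = 5. These figures assume independent reads at a fixed 90% accuracy, and that accuracy is recomputed within the category, which is the natural reading of the SAP but is not stated outright. How often such cells will arise cannot be determined from the documents. The gap at exactly 70% is a plain drafting defect that needs no assumption.

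This is a minor improvement to a secondary descriptive output. The primary pooled estimates and their intervals are unaffected.

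**What to change.** In SAP 8.6:

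1. Derive each reader's band once, from all of that reader's classified images. Report bands only for country, specialty, training method and prior scan count. Drop them for certainty levels and for the prospective/retrospective split. For time from training, show pooled image-level accuracy with its interval and no bands.
2. Itemise the by-reader table already promised in the protocol abstract, Protocol 9.5 and SAP 5, with each reader's correct/total and exact 95% interval, and refer to it beside the band table.
3. Close the gap at 70%, for example by making the lowest band 70% or less, which matches the closed upper limits of the two middle bands.

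A minimum image count for banding is optional. Any threshold is a judgement, and it would leave low-volume readers out of the counts.

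The cost is SAP and table-shell wording, with no new data. SAP 9, which now declares no change from the protocol's analysis, would need to record the dropped band tables. The downside is fewer band tables; image-level accuracy by certainty and data source would still be reported with intervals.

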9.8 Quality Control

9.8.1 Mechanisms and Procedures to Ensure Data Quality and Integrity

For eCRFs, data will be entered by trained site personnel with reasons given for any missing data. Any errors should be corrected within the electronic system. The audit trail will record all changes made, the date and time of the correction, and the person correcting the error. The appropriate electronic signature will be provided. Any data recorded directly in the eCRF, for which no other written or electronic record will be maintained in the subject's medical record, will be considered source data and should be signed by the investigator(s). Data collected from sites via eCRFs will be subject to source verification and edit checks for completeness, consistency, and logic.

GE Confidential Page 31 of 43

Audit and Inspection

The Sponsor will ensure that the analytical dataset and statistical programmes used for generating the data included in the final study report are kept in electronic format and are available for auditing and inspection.

According to International Conference on Harmonization (ICH) E6-Good Clinical Practice (GCP), the Sponsor or regulatory authorities may audit the investigational site. The Sponsor's Quality Assurance Unit, independent of the Clinical Research and Development Department, is responsible for auditing the study.

The investigator(s) must accept that regulatory authorities may conduct an inspection to verify compliance of the study with GCP.

Confidentiality Regarding Study Subjects

The investigator(s) must assure that the privacy of the subjects, including their personal identity and all other personal medical information, will be maintained at all times. In eCRFs and other documents or image material (including materials from all examinations, e.g., CT, PET, and MRI examinations) submitted to the Sponsor/CRO, subjects will not be identified by their names, but by an identification code (e.g., study subject number).

Personal medical information may be scrutinised for the purpose of verifying data recorded in the eCRF. This may be done by the monitor(s), properly authorised persons on behalf of the Sponsor, the quality assurance unit, or regulatory authorities. Personal medical information will always be treated as confidential.

9.8.2 Source Data Verification

Source data verification will be conducted by the CRO. The monitor(s), auditor(s), authorised personnel of the Sponsor/CRO, health authority inspector(s) or their agents, and authorised members of the IECs will be given direct access to source data and documentation (e.g., medical charts/records, laboratory results, printouts, videotapes, etc.) for source data verification, provided that subject confidentiality is maintained in accordance with local requirements. Image evaluation data from the clinical readers and expert readers will be entered directly into the eCRF and so no source verification is required.

